7.2. Screening and Critical Baseline Assessments

Cardiovascular medical history/risk factors (as detailed in the eCRF) will be assessed at Screening.

The following demographic parameters will be captured: year of birth, sex, race, and ethnicity.

Medical/medication/family history will be assessed as related to the inclusion/exclusion criteria listed in Section 5.

7.3. Safety

Planned time points for all safety assessments are listed in the Time and Events Tables (Section 7.1). Additional time points for safety tests such as vital signs, physical exams and laboratory safety tests may be added during the course of the study based on newly available data to ensure appropriate safety monitoring.

7.3.1. Adverse Events and Serious Adverse Events

The definitions of an AE or an SAE can be found in [Appendix 5](#).

The investigator and their designees are responsible for detecting, documenting, and reporting events that meet the definition of an AE or SAE.

7.3.1.1. Time period and Frequency for collecting Adverse Event and Serious Adverse Event information

- Any SAEs assessed as related to study participation (e.g., protocol-mandated procedures, invasive tests, or change in existing therapy) or related to a GSK product will be recorded from the time a subject consents to participate in the study up to and including any follow-up contact.
- AEs and SAEs will be collected from the time informed consent is obtained until the follow-up contact (see Section 7.3.1.3) at the time points specified in the Time and Events Tables (Section 7.1).
- Medical occurrences that begin prior to the start of study treatment but after obtaining informed consent may be recorded on the Medical History/Current Medical Conditions section of the eCRF.
- All SAEs will be recorded and reported to GSK within 24 hours, as indicated in [Appendix 5](#).
- Investigators are not obligated to actively seek AEs or SAEs in former study subjects. However, if the investigator learns of any SAE, including a death, at any time after a subject has been discharged from the study, and he/she considers the event reasonably related to the study treatment or study participation, the investigator must promptly notify GSK.

NOTE: The method of recording, evaluating and assessing causality of AEs and SAEs plus procedures for completing and transmitting SAE reports to GSK are provided in [Appendix 5](#).

7.3.1.2. Method of Detecting Adverse Events and Serious Adverse Events

Care will be taken to not introduce bias when detecting AEs and/or SAEs. Open-ended and nonleading verbal questioning of the subject is the preferred method to inquire about an AE occurrence. Appropriate questions include:

- “How are you feeling?”
- “Have you had any (other) medical problems since your last visit/contact?”
- “Have you taken any new medicines, other than those provided in this study, since your last visit/contact?”

7.3.1.3. Follow-up of Adverse Events and Serious Adverse Events

After the initial AE/SAE report, the investigator is required to proactively follow each subject at subsequent visits/contacts. All SAEs, and nonserious AEs of special interest (as defined in Section 4.6.1) will be followed until resolution, until the condition stabilizes, until the event is otherwise explained, or until the subject is lost to follow-up (as defined in Section 5.4). Further information on follow-up procedures is given in [Appendix 5](#).

7.3.1.4. Regulatory Reporting Requirements for Serious Adverse Events

Prompt notification by the investigator to GSK of SAEs and nonserious AEs related to study treatment (even for noninterventional postmarketing studies) is essential so that legal obligations and ethical responsibilities towards the safety of subjects and the safety of a product under clinical investigation are met.

GSK has a legal responsibility to notify both the local regulatory authority and other regulatory agencies about the safety of a product under clinical investigation. GSK will comply with country specific regulatory requirements relating to safety reporting to the regulatory authority, IRB/IEC, and investigators.

Investigator safety reports are prepared for suspected unexpected serious adverse reactions according to local regulatory requirements and GSK policy and are forwarded to investigators as necessary.

An investigator who receives an investigator safety report describing an SAE(s) or other specific safety information (e.g., summary or listing of SAEs) from GSK will file it with the IB and will notify the IRB/IEC, if appropriate according to local requirements.

7.3.2. Pregnancy

- Details of all pregnancies in female subjects and, if indicated, female partners of male subjects will be collected after the start of dosing and until 7 days post-last dose.

- If a pregnancy is reported then the investigator should inform GSK within 2 weeks of learning of the pregnancy and should follow the procedures outlined in [Appendix 7](#).

7.3.3. Physical Exams

- A complete physical examination will include, at a minimum, assessment of the cardiovascular, respiratory, GI, and neurological systems. Height and weight will also be measured and recorded.
- A brief physical examination will include, at a minimum, assessments of the skin, lungs, cardiovascular system, and abdomen (liver and spleen).
- Investigators should pay special attention to clinical signs related to previous serious illnesses

7.3.4. Vital Signs

- Vital signs will be measured in semi-supine position after 5 minutes rest and will include systolic and diastolic blood pressure, and pulse rate. Baseline body temperature and respiratory rate will be collected at Screening only.

7.3.5. Electrocardiogram

- Single 12-lead ECGs will be obtained at each time point during the study using an ECG machine that automatically calculates the heart rate and measures PR, QRS, QT, and QTc intervals. Refer to Section [5.4.2](#) for QTc withdrawal criteria and additional QTc readings that may be necessary.

7.3.6. Clinical Safety Laboratory Assessments

All protocol required laboratory assessments, as defined in [Table 6](#), must be conducted in accordance with the Laboratory Manual, and Protocol Time and Events Tables (Section [7](#)). Laboratory requisition forms must be completed and samples must be clearly labelled with the subject number, protocol number, clinic number, and visit date. Details for the preparation and shipment of samples will be provided by the laboratory and are detailed in the SRM. Reference ranges for all safety parameters will be provided to the clinic by the laboratory responsible for the assessments.

If additional nonprotocol specified laboratory assessments are performed at the institution's local laboratory and result in a change in subject management or are considered clinically significant by the investigator (e.g., SAE or AE or dose modification) the results must be recorded in the eCRF.

Refer to the SRM for appropriate processing and handling of samples to avoid duplicate and/or additional blood draws.

Hematology, serum chemistry, urinalysis, and additional parameters to be tested are listed in [Table 6](#).

Table 6 Laboratory Assessments

Hematology			
Platelet Count	RBC Indices:	WBC count with Differential:	
RBC Count	MCV	Neutrophils	
Hemoglobin	MCH	Lymphocytes	
Hematocrit	MCHC	Monocytes	
		Eosinophils	
		Basophils	
Serum Chemistry^a			
Blood urea nitrogen	Potassium	AST	Total and direct bilirubin
Creatinine	Sodium	ALT	Total protein
Glucose	Calcium	Alkaline phosphatase	Albumin
Creatine kinase			
Routine Urinalysis			
Specific gravity			
pH, glucose, protein, blood, and ketones by dipstick			
Microscopic examination (if blood or protein is abnormal)			
Other Screening Tests			
eGFR (Section 6.2)			
Clcr (Section 6.2)			
Hepatitis B surface antigen, hepatitis C antibody, and human immunodeficiency virus			
Follicle-stimulating hormone and estradiol (as needed in women of nonchildbearing potential only)			
Serum test for human chorionic gonadotropin (as needed in women of childbearing potential)			
Alcohol (via urine, blood alcohol, or breathalyzer test) and drug screen (via serum, urine, or saliva) to include, at a minimum: amphetamines, barbiturates, cocaine, opiates, cannabinoids, and benzodiazepines).			

^a Details of liver chemistry stopping criteria and required actions and follow-up assessments after liver stopping or monitoring event are given in Section [5.4.1](#) and [Appendix 3](#).

All laboratory tests with values that are considered clinically significantly abnormal during participation should be repeated until the values return to normal or baseline. If such values do not return to normal within a period judged reasonable by the investigator, the etiology should be identified and the sponsor notified.

7.4. Pharmacokinetics

7.4.1. Blood Sample Collection

The PK blood samples for the analysis of gepotidacin will be collected at the time points listed in Section [7.1](#), Time and Events Tables. The actual date and time of each blood sample collection will be recorded. The timing of PK samples may be altered and/or PK samples may be obtained at additional time points to ensure thorough PK monitoring.

For each sample, 3 mL of blood will be drawn via an indwelling catheter and/or direct venipuncture into tubes containing ethylenediaminetetraacetate anticoagulant. Details of PK blood sample processing, storage, and shipping procedures are provided in the SRM.

7.4.2. Urine Sample Collection

The PK urine samples for the analysis of gepotidacin will be collected at the time points listed in Section 7.1, Time and Events Tables. The actual date and time of each urine sample collection will be recorded. The timing of PK samples may be altered and/or PK samples may be obtained at additional time points to ensure thorough PK monitoring.

Details of PK urine sample processing, storage, and shipping procedures are provided in the SRM.

7.4.3. Saliva Sample Collection

The PK saliva samples for parent analysis of gepotidacin will be collected from subjects in Part 1 at the time points listed in Section 7.1, Time and Events Tables. The timing of saliva samples may be altered and/or samples may be obtained at additional time points to ensure thorough PK monitoring.

Details of PK saliva sample collection, processing, storage, and shipping procedures are provided in the SRM.

7.4.4. Dialysate Sample Collection

The PK dialysate samples for analysis of gepotidacin will be collected at the time points listed in Section 7.1, Time and Events Tables (Table 4 and Table 5; Group F only). The timing of dialysate samples may be altered and/or samples may be obtained at additional time points to ensure thorough PK monitoring.

Details of PK dialysate sample collection, processing, storage, and shipping procedures are provided in the SRM.

7.4.5. Sample Analysis

Plasma, urine, saliva, and dialysate analysis will be performed under the control of PTS-DMPK/Scinovo, GSK, the details of which will be included in the SRM. Concentrations of gepotidacin will be determined in plasma, urine, saliva, and dialysate samples using the currently approved bioanalytical methodology. Raw data will be archived at the bioanalytical site (detailed in the SRM).

Since plasma protein binding of gepotidacin is low (33%), only total drug concentrations will be reported for the PK analysis.

Once the plasma, urine, saliva, and dialysate have been analyzed for gepotidacin, any remaining plasma, urine, saliva, and dialysate may be analyzed for other compound-related metabolites and the results reported under a separate PTS-DMPK/Scinovo, GSK protocol.

7.5. Optional Pharmacokinetic Markers

With the subject's consent, if a kidney or bladder tissue sample is collected for a nonstudy purpose, excess tissue may be collected during this study and may be used for the purposes of measuring drug concentrations of gepotidacin.

7.6. Genetics

Depending on the clinical study results, optional exploratory pharmacogenomics analyses may be performed to examine the potential relationship between genetic variants and clinical endpoints.

The pharmacogenomics samples will be collected according to the Time and Events Tables ([Table 2](#) and [Table 4](#)). Information regarding genetic research is included in [Appendix 4](#).

8. DATA MANAGEMENT

- For this study, subject data will be entered via an eCRF into Oracle Clinical Remote Data Capture System. Subject data will be available for viewing through access to the Oracle Clinical Remote Data Capture System. Data provided from other sources will be received, reconciled, combined, and transferred to GSK at predetermined time points.
- Management of clinical data will be performed in accordance with applicable PPD standards and data cleaning procedures to ensure the integrity and quality of the data (e.g., removing errors and inconsistencies in the data). Adverse events and concomitant medications terms will be coded using Medical Dictionary for Regulatory Activities (MedDRA) and a validated medication dictionary, GSKDrug.
- The eCRFs (including queries and audit trails) will be sent at the end of the study in electronic format to GSK to be retained. Each investigator will receive a copy of their site specific data in the same format to maintain as the investigator copy. In all cases, subject initials will not be collected or transmitted.

9. STATISTICAL CONSIDERATIONS AND DATA ANALYSES

9.1. Hypotheses

A formal hypothesis will not be tested; however, an estimation approach will be taken to characterize the PK of gepotidacin in subjects with mild, moderate, severe renal impairment and in subjects with ESRD (on dialysis and not on dialysis) compared with matched subjects with normal renal function.

9.2. Sample Size Considerations

9.2.1. Sample Size Assumptions

The target sample size of 16 evaluable subjects with normal renal function and 8 evaluable renally impaired subjects was chosen based on feasibility, to address the objectives of the study. This sample size is considered sufficient to determine whether the pharmacokinetics in subjects with renal impairment is meaningfully different from subjects with normal renal function.

The between-subject variations of PK parameters from 1000 mg 2-hour IV administration on Day 1 in the BTZ115198 study were 26.3%, 27.4%, and 27.6% for the C_{max}, from AUC from time 0 to infinity (AUC(0-∞)), and AUC(0-t), respectively [see report of Study BTZ115198].

For a between-subject coefficient of variation of 26.3%, 27.4%, and 27.6%, and a sample size of 16 subjects for the subjects with normal renal function and 8 subjects for the renally impaired group, it is estimated that the half width of the 90% confidence interval (CI) for the difference on log-scale will be within 21.77%, 22.75%, and 23.00% of the point estimate for C_{max}, AUC(0-∞), and AUC(0-t), respectively.

9.2.2. Sample Size Re-estimation or Adjustment

Not applicable.

9.3. Data Analysis Considerations

In general, descriptive summaries will include number of subjects (n), mean, SD, median, minimum, and maximum for continuous variables; and percent for categorical variables. Summaries will present data by group, and where appropriate, by assessment time.

9.3.1. Analysis Populations

The **Safety Population** will consist of all subjects who receive at least 1 dose of study drug and have at least one postdose safety assessment.

The **PK Population** will consist of all subjects who received at least 1 dose of gepotidacin and have evaluable PK data for gepotidacin.

The **PK Parameter Population** will consist of all subjects in the PK Population, for whom valid and evaluable PK parameters were derived. This population will be used in the assessment and characterization of PK parameters.

9.3.2. Interim Analysis

No formal interim analyses are planned for this study. However, all preliminary safety, tolerability, and available PK data will be reviewed internally at GSK after the approximate sample size has been reached in Part 1 and Part 2 (optional).

9.4. Key Elements of Analysis Plan

9.4.1. Primary Analyses

Pharmacokinetic Analyses

Plasma, urine, and saliva concentrations of gepotidacin will be subjected to PK analyses using noncompartmental methods. Based on the individual concentration time data the following parameters will be estimated:

Plasma:

AUC(0-∞)	Area under the concentration-time curve from time 0 (predose) extrapolated to infinite time
AUC(0-t)	Area under the concentration-time curve from time 0 (predose) to time of last quantifiable concentration
CL	Systemic clearance
C _{max}	Maximum observed concentration
λ _z	Terminal-phase rate constant
t _{1/2}	Terminal phase half life
T _{max}	Time to first occurrence of C _{max}
V _{ss}	Volume of distribution at steady-state of parent drug
V _z	Volume of distribution of the terminal phase

Urine:

A _e total	Total unchanged drug (total amount of drug excreted in urine), calculated by adding all the fractions of drug collected over all the allotted time intervals
A _e (t ₁ -t ₂)	Amount of drug excreted in urine in a time intervals for predose, 0 to 6, 6 to 12, 12 to 24, or 24 to 36, and 36 to 48 hours after dosing for subjects with renal impairment; and predose, 0 to 2 hours, 2 to 4 hours, 4 to 6 hours, 6 to 8 hours, 8 to 12 hours, 12 to 24 hours, 24 to 36 hours, and 36 to 48 hours for subjects with normal renal function
fe%	Percentage of the given dose of drug excreted in urine, calculated as: fe% = (A _e total/Dose) × 100
CL _r	Renal clearance of drug, calculated as: A _e total/AUC(0-t)

Dialysate (Subjects with ESRD on dialysis; Group F subjects in Part 2):

A _{rem} (0-1)	Amount of drug removed by hemodialysis from time 0 to 1 hour after the start of hemodialysis
A _{rem} (1-2)	Amount of drug removed by hemodialysis from time 1 to 2 hours after the start of hemodialysis

Arem(2-3)	Amount of drug removed by hemodialysis from time 2 to 3 hours after the start of hemodialysis
Arem(3-4)	Amount of drug removed by hemodialysis from time 3 to 4 hours after the start of hemodialysis (or to the end of dialysis if less than 4 hours)
Arem(0-4)	Cumulative amount of drug removed by hemodialysis from time 0 to 4 hours after the start of hemodialysis (or to the end of dialysis if less than 4 hours)
AUC(t0-t1)	Partial area under the curve estimated from predialyzer samples collected from start of dialysis (t0) to end of dialysis (t1)
CL _D	Dialysis clearance, calculated as the total amount of the analyte recovered in the dialysate over 4 hours (or the total dialysis interval if less than 4 hours) divided by the partial area under the curve during the period of dialysis, which will be calculated using the predialyzer samples
Frem%(0-4)	Fraction (%) of the dose removed by hemodialysis from 0 to 4 hours after the start of hemodialysis (or to the end of dialysis if less than 4 hours)

Plasma concentrations (all subjects), urine concentrations, and dialysate concentrations (Group F) of gepotidacin and the associated PK parameters will be listed, and summary statistics (n, mean, median, standard deviation [SD], minimum, maximum, and coefficient of variation [CV]) will be presented by day and treatment. Mean and individual plasma concentration versus time profiles will be presented graphically on linear and semilogarithmic scales.

The log-transformed AUC(0-∞), AUC(0-t), and C_{max} values for gepotidacin in the renal impairment groups and normal renal function groups will be compared using an analysis of variance. Geometric mean ratios between renal impairment groups and normal renal function groups, and 90% CIs for the ratios of AUC(0-∞) and C_{max} for gepotidacin will be presented.

Linear regression analysis will be used to evaluate the relationships between estimated renal function and relevant PK parameters (e.g., AUC, C_{max}, and CL). If the data permit the identification of linear functions that fit the data well, the resulting slopes will provide a comparison of any difference in the response of the gepotidacin IV treatment as renal function changes.

If the appropriate number of subjects with severe renal impairment and/or subjects with ESRD not on dialysis cannot be enrolled, or their eGFR values cluster at the higher end of the range, the PK profiles in subjects with ESRD on hemodialysis may be modeled to understand the pharmacokinetics for the other groups of subjects with renal impairment at the lower end of the range (<15 mL/min/1.73 m²), as well as for subjects with ESRD not on hemodialysis.

Detailed descriptions of the analyses in this study will be presented in the Reporting and Analysis Plan (RAP).

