3. OBJECTIVES AND ENDPOINTS

Objectives	Endpoints
Primary	

 To compare the pharmacokinetics of gepotidacin administered as a 750-mg IV dose in normal healthy subjects compared with subjects with mild, moderate, and severe renal impairment, and with subjects with end-stage renal disease (ESRD) 	
 Plasma primary pharmacokinetic (PK) endpoints include AUC(0-∞) and Cmax of gepotidacin, as data permit Urine primary PK end points include Ae total, fe%, and CLr of gepotidacin, as data permit Dialysate primary PK end points include AUC(t0-t1), CLD, and Frem%(0-4), of gepotidacin, as data permit
Secondary	

 To assess the safety and tolerability of gepotidacin administered as a 750-mg IV dose in normal healthy subjects compared with subjects with mild, moderate, severe renal impairment, and with subjects with ESRD 	
 12-lead safety electrocardiogram readings, change from baseline in vital sign measurements (blood pressure and heart rate), monitoring of adverse events, toxicity grading of clinical laboratory test results, and physical examinations

 To evaluate the secondary PK parameters of gepotidacin administered as a 750-mg IV dose in normal healthy subjects compared with subjects with mild, moderate, and severe renal impairment, and with subjects with ESRD 	
 Plasma PK endpoints include AUC(0-t), CL, λz, t1/2, Tmax, Vss, and Vz, as data permit Urine PK endpoint includes Ae(t1-t2), as data permit Dialysate PK endpoints include Arem(0-1), Arem(1-2), Arem(2-3), Arem(3-4), and Arem(0-4), as data permit
Exploratory	

 To evaluate the saliva pharmacokinetics of gepotidacin (subjects in Part 1 only) 	
 Primary PK endpoints include AUC(0-∞) and Cmax of gepotidacin, as data permit Secondary PK endpoints include AUC(0-t), CL, λz, t1/2, Tmax, Vss, and Vz, as data permit

ESRD = end-stage renal disease; PK = pharmacokinetic

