5.1. Inclusion Criteria

A subject will be eligible for inclusion in this study only if all of the following criteria apply:

AGE
1. Male or female subject between 18 and 80 years of age, inclusive.

TYPE OF SUBJECT AND DIAGNOSIS INCLUDING DISEASE SEVERITY
2. Healthy subject must be in clinically stable health as determined by the investigator based on medical history, clinical laboratory results (serum chemistry, hematology, urinalysis, and serology), vital sign measurements, 12-lead electrocardiogram (ECG) results, and physical examination findings. Subject with renal impairment must have clinical laboratory values consistent with their disease and are approved by the investigator.
3. Subject with renal impairment (mild, moderate, severe, or subjects with ESRD) may be taking medications, which in the opinion of the investigator, are believed to be therapeutic but do not affect study drug absorption, distribution, metabolism, or excretion. These medications must be stable doses taken for at least 7 days before the first dose of study drug. Any exceptions will be discussed with the sponsor or medical

monitor on a case-by-case basis and the reasons documented.

4. Subject with normal renal function or renal impairment (estimated eGFR corresponding to the calculated eGFR [the estimated eGFR may be rounded to the nearest integer]) at Screening (Section 6.2).
5. Subjects with ESRD on hemodialysis should be on hemodialysis for at least 3 months before Screening and is able to tolerate a hemodialysis treatment lasting 3 to 4 hours with blood flow rates of >200 mL/min.
6. Alanine aminotransferase (ALT) and bilirubin $1.5 \times$ upper limit of normal (ULN; isolated bilirubin >math>1.5 \times</math> ULN is acceptable, if bilirubin is fractionated and direct bilirubin <math><35\%</math>).

WEIGHT

7. Body weight ≥ 50 kg and BMI within the range 18.5 and 40 kg/m², inclusive.

SEX

8. Male or Female

A female subject is eligible to participate if she is not pregnant (as confirmed by a negative serum human chorionic gonadotrophin test), not lactating, and at least one of the following conditions applies:

- a Nonreproductive potential defined as:
 - Premenopausal females with one of the following:
 - Documented tubal ligation
 - Documented hysteroscopic tubal occlusion procedure with follow-up confirmation of bilateral tubal occlusion
 - Hysterectomy
 - Documented bilateral oophorectomy

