**Table 6 Derived Dialysate Pharmacokinetic Parameters**

Parameter	Parameter Description
Arem(0-1)	Amount of drug removed by hemodialysis from time 0 to 1 hours after the start of hemodialysis
Arem(1-2)	Amount of drug removed by hemodialysis from time 1 to 2 hours after the start of hemodialysis
Arem(2-3)	Amount of drug removed by hemodialysis from time 2 to 3 hours after the start of hemodialysis
Arem(3-4)	Amount of drug removed by hemodialysis from time 3 to 4 hours after the start of hemodialysis (or to the end of dialysis if less than 4 hours)
Arem(0-4)	Cumulative amount of drug removed by hemodialysis from time 0 to 4 hours after the start of hemodialysis (or to the end of dialysis if less than 4 hours)
AUC(t0-t1)	Partial area under the curve estimated from predialyzer samples collected from start of dialysis (t0) to end of dialysis (t1)
CLD	Dialysis clearance, calculated as the total amount of the analyte recovered in the dialysate over 4 hours (or the total dialysis interval if less than 4 hours) divided by the partial area under the curve during the period of dialysis, which will be calculated using the predialyzer samples
Frem%(0-4)	Fraction (%) of the dose removed by hemodialysis from 0 to 4 hours after the start of hemodialysis (or to the end of dialysis if less than 4 hours)

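### For a dialysis session longer than 4 hours, CLD divides drug recovered in the first 4 hours by plasma AUC over the whole session and so comes out too low; sessions of 4 hours or less are unaffected.

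*Protocol*

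**What the plan says.** CLD is a primary endpoint for the dialysate data. Protocol Section 3 states: "Dialysate primary PK end points include AUC(t0-t1), CLD, and Frem%(0-4), of gepotidacin, as data permit".

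Protocol 9.4.1 defines the CLD numerator as "the total amount of the analyte recovered in the dialysate over 4 hours (or the total dialysis interval if less than 4 hours"). Its window is therefore the shorter of 4 hours and the session length.

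SAP Table 6 repeats that numerator and, like the protocol, completes the formula as "divided by the partial area under the curve during the period of dialysis, which will be calculated using the predialyzer samples". Only one such partial AUC is defined in either document, AUC(t0-t1): "Partial area under the curve estimated from predialyzer samples collected from start of dialysis (t0) to end of dialysis (t1"). It has no 4-hour limit.

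On session length, inclusion criterion 5 (Protocol 5.1) asks that a Group F subject "is able to tolerate a hemodialysis treatment lasting 3 to 4 hours". That is a tolerance requirement and does not set a maximum. Protocol Table 5, footnote f, collects dialysate hourly through the session in Period 1 and names no stopping hour. SAP 2.1 declares no change from the protocol's planned analysis.

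**The concern.** Amount recovered divided by AUC is a clearance only when both terms cover the same stretch of time. The plan provides for sessions shorter than 4 hours in Arem(3-4), Arem(0-4), CLD and Frem%(0-4), but has no matching provision for longer ones. Once a session passes 4 hours, the numerator stops growing while the denominator continues.

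CLD is meant to describe how well the dialyzer clears the drug, largely independent of how long the session lasts. As written, two subjects with identical dialyzer clearance would get different values if one session ran over. Every overrun moves CLD in the same direction, so the errors do not cancel. With about 4 to 8 subjects, one or two overruns could shift the group summary and add spread that reflects session length.

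**Working it through.** The documents give no numerical CLD, so there is no figure to reproduce. The check works from the definition.

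**Inputs from the documents**
- Numerator window: min(4 h, T), where T is session length (Protocol 9.4.1, SAP Table 6).
- Denominator window: 0 to T, start to end of dialysis (same places).
- Total clearance 43 L/h, renal clearance 16 L/h, Vdss 1.30 (Protocol Appendix 11). These serve only to choose an illustrative half-life.

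**Assumptions**
- Dialyzer clearance is constant and plasma concentration declines mono-exponentially during dialysis, with half-life between 1.5 and 12 h.
- For the illustrative value, Vdss is in L/kg and body weight is 70 kg.

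**Formula.** With constant clearance, the amount recovered over a window equals true CLD times the AUC over that window. Hence

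reported CLD / true CLD = AUC(0 to min(4, T)) / AUC(0 to T) = (1 − exp(−k·min(4, T))) / (1 − exp(−k·T)), with k = ln 2 / half-life.

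For T ≤ 4 h this is exactly 1. For T > 4 h it is below 1 whenever concentrations after hour 4 are positive, whatever the shape of the curve.

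**Illustrative half-life.** Nonrenal clearance is 43 − 16 = 27 L/h. Volume is 1.30 × 70 = 91 L. Half-life without dialysis is ln 2 × 91 / 27 = 2.34 h, about 2.3 h. Adding an assumed dialysis clearance of 5 or 10 L/h gives 1.97 or 1.70 h, still inside the range used.

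**Numbers put in at 2.3 h.** k = 0.6931 / 2.3 = 0.3014.
- T = 4.5 h: 0.70045 / 0.74235 = 0.944
- T = 5 h: 0.70045 / 0.77839 = 0.900

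A true CLD of 10 L/h would be reported as 9.44 L/h and 9.00 L/h.

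**Reported / true CLD over the range**

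| Half-life on dialysis | T ≤ 4 h | T = 4.25 h | T = 4.5 h | T = 5 h |
|---|---|---|---|---|
| 1.5 h | 1.000 | 0.980 | 0.963 | 0.935 |
| 2.3 h | 1.000 | 0.970 | 0.944 | 0.900 |
| 4 h | 1.000 | 0.959 | 0.923 | 0.863 |
| 6 h | 1.000 | 0.954 | 0.913 | 0.843 |
| 12 h | 1.000 | 0.948 | 0.901 | 0.822 |

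The shortfall is therefore about 2% to 5% at 4.25 h, 4% to 10% at 4.5 h and 6.5% to 18% at 5 h. When both terms share a window, the ratio is 1.000 for every T.

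**The case against.** The strongest reply is that the plan does not contemplate a session over 4 hours. The only session length in either document is 3 to 4 hours, and every amount-removed parameter ends at hour 4. The blood schedule fits as well. In Period 1 dialysis starts about 2 hours after the start of infusion, so the 6-hour sample falls at about hour 4 of dialysis. The next, at 8 hours, falls at about hour 6, so no end-of-session sample is scheduled for a 4.5 or 5 hour session. Collection details are also deferred to the Study Reference Manual, which is not available here and may contain an operating rule.

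Most of this stands. It limits the point to a contingency: in the planned case there is no error, and nothing in the documents shows that overruns are expected. It does not remove the point. Criterion 5 is not a cap, and SAP 7.1.3.1 bases noncompartmental calculations on actual sampling times, so an overrun would not simply be treated as 4 hours. Reading the period of dialysis as the first 4 hours conflicts with the plan's own definition of t1.

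The size can also be challenged. The 18% figure needs both a 5-hour session and a 12-hour half-life, neither of which is in the documents. Dialysis begins near peak concentration, so a distribution phase would put more of the AUC early and shrink the bias relative to a mono-exponential curve with the same later decline. Both remarks are fair. They affect the size and leave the direction unchanged.

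A reader might infer that the plan understates drug removal by hemodialysis generally. The documents do not support that: Arem(0-4) and Frem%(0-4) are labelled as 0 to 4 hour quantities and have no AUC denominator. Nor do they establish that dialysate data are thrown away. Footnote f leaves collection after hour 4 possible, but no interval beyond hour 4 is named.

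**Conclusion.** The mismatch is in the text of both documents, and for any session over 4 hours it makes CLD too low. The direction needs only constant dialyzer clearance and measurable drug after hour 4. The size rests on the assumed half-lives and session lengths: about 6% at 4.5 hours and 10% at 5 hours for the illustrative 2.3-hour half-life, within the wider ranges shown above.

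The practical weight is small. Sessions of 4 hours or less are unaffected. Group F is optional, with about 4 to 8 subjects, and dialysate is collected in Period 1 only. CLD is listed and summarised; SAP 7.1.3.2 specifies no model for it, no hypothesis is tested, and no decision rule uses it. It would be wrong to conclude that the Group F clearance result is biased as planned. The case for acting is that this is a primary dialysate endpoint and the correction costs almost nothing.

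**What to change.** In Protocol 9.4.1 and SAP Table 6, define CLD = Arem(0-τ) / AUC(t0 to t0+τ), with the same τ in both terms, where τ is the earlier of 4 hours and the actual end of dialysis. State that a final part-hour collection counts, so that a session ending at, say, 3.5 hours keeps all its recovered drug, as the present text intends. AUC(t0-t1) to the end of dialysis can still be reported as a separate endpoint.

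The cost is one sentence in each document. It needs no extra subjects, samples or change to the dialysis session. If dialysis starts on schedule, the 4-hour limit coincides with the 6-hour blood sample already planned. Values for sessions of 4 hours or less stay the same.
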